3.3 Early Withdrawal of Subjects

3.3.1 Criteria for removal from study

Subjects will be removed from the study for safety reasons. Subjects will be evaluated for potential negative reactions to study medications at each visit. Additionally, subjects will be advised to contact the study team immediately with any new negative symptoms.

Known severe adverse events of the study drugs will result in the immediate cessation of the study drugs and removal from the study.

- 1. Severe adverse events of NETA include:
 - a. (1) Stroke (2) Deep Vein Thrombosis (3) Pulmonary Embolism (4) Myocardial Infarction (5) Retinal Vein Thrombosis.
 - b. Worsening or persistent migraines will result in cessation of the study drug and therefore, removal from the study.
- 2. Serious adverse events associated with CBD include:
 - a. (1) Suicidal ideation (2) Liver Dysfunction resulting in hepatic failure, hepatic pain that limits self-care activities of daily living, or acute liver damage as measured by LFTS (elevations in ALT or AST > 3 times the ULN and for ALP or TBL > 2 times the ULN)

In the case of an inadvertent pregnancy, the study participant will be immediately withdrawn from the study.

Other adverse events will be monitored and may result in cessation of the study drug and subject withdrawal from the study as determined by the clinical investigator. When possible, we will use the definitions described by the NIH's Common Terminology Criteria for Adverse Events (CTCAE), Version 5, subjects meeting criteria for a Grade 3 CTCAE will be withdrawn from the study if they can be attributed to the study drug. If causality cannot be determined, it will be attributed to the study drug.

Examples:AnemiaGrade 3Hb < 8.0	DiarrheaGrade 3Increase of \geq 7 stools per day over baseline

Withdrawal of consent at any time during the study period will also constitute the withdrawal of a study subject.

3.3.2 Follow-up for withdrawn subjects

Subjects will be asked to return the study drug to the site if withdrawn from the study.

If the subject was removed for elevated LFTS, these will be followed until resolution and the patient advised to seek medical care if appropriate. If the subject is removed from the study for any of the other reasons as described in 3.3.1, she will receive the appropriate treatment and follow up based on the decision of her providing physician team.

In the case of an inadvertent pregnancy, the study participant will be immediately withdrawn from the study. The participant will be followed through during pregnancy for adverse maternal, fetal and neonatal outcomes that could be appropriately linked back to the study drug.

No further data will be collected on these patients and the subject will not be replaced.

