7.2.4 Study Visit 3 – 4 week treatment

The subject will return in 4 weeks for a follow up visit. The study visit window will be 3 days before or 3 days after this time to account for weekends. At this time the subject will be given time to ask any questions or voice any concerns they may have had over the past 4 weeks, reviewing and recording any adverse events. The subject's compliance with daily surveys and study drug will be reviewed.

A physical assessment will be performed as detailed in Section 7.2.3. Subjects who experience severe adverse events will be instructed to stop the study drug and withdraw from the study. Please refer to Section 3.3.1.

The subject will be given another 1 month supply of the study drug and NETA as needed. As stated above, NETA dosage will be adjusted as necessary.

The subject will also complete the following surveys: (1) EHP-30 (2) PGA (3) PGIC (4) C-SSRS (5) FSFI (if partnered and sexually active) on-site prior to being discharged from the visit. The following bloodwork will be obtained: (1) Inflammatory markers (2) Monitoring LFTS. Approximately 1-2 teaspoons of blood will be drawn at this visit.

They will be required to bring all medication bottles to the visit. Oxycodone, if prescribed, and NETA pills will be counted and recorded. Additional refills will be provided as needed. The study drug bottle and NETA will be inspected and returned to the clinician. The patient will be provided with a new supply of study drug and NETA at this time.

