9.3 Method of collection of safety information

Study data will be managed using RedCap, a secure web application designed to support data capture for research studies. Well-designed data collection forms will be developed to minimize data collection and recording errors; forms will be designed to collect longitudinal and cumulative information regarding adverse events and concomitant medication usage.

Adverse events will be categorized and patients experiencing adverse events during the treatment will be recorded in RedCap. Patient's will be potentially removed from the study if deemed medically necessary. The principle investigator and IRB will be notified immediately of serious adverse effects.

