18.7 Stopping Rules

The principle investigator will receive immediate notification of all serious adverse events. The principle investigator will meet with the research team after the receipt of any report of any major serious adverse event and determine whether the participant will need to be removed from the study or whether the study should be paused until further investigation.

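### Outcome collection ends when a woman is removed from the study for safety, so pain over the full 8 weeks and her remaining questionnaires cannot be recovered

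*Combined protocol and SAP*

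**What the plan says.** Section 3.3.1 ties stopping treatment to leaving the study. For the listed events: "Known severe adverse events of the study drugs will result in the immediate cessation of the study drugs and removal from the study". For migraine: "Worsening or persistent migraines will result in cessation of the study drug and therefore, removal from the study". Grade 3 CTCAE events attributed to study drug also lead to withdrawal, with a default on attribution: "If causality cannot be determined, it will be attributed to the study drug". Section 7.2.4 repeats the link at Visit 3: "Subjects who experience severe adverse events will be instructed to stop the study drug and withdraw from the study". For other adverse events, 3.3.1 leaves the decision to the clinical investigator.

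Section 3.3.2 keeps liver-test follow-up to resolution, pregnancy outcomes, and whatever care the woman's physicians choose. It closes with: "No further data will be collected on these patients and the subject will not be replaced".

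Section 8.3 compares arms on the AUC of daily VAS over the 8-week intervention period. It rescales each woman's AUC to a 7-day average so that early withdrawals can be included. The same paragraph describes endometriosis pain as cyclic. Secondary endpoints are changes from baseline. Section 7.1 schedules questionnaires and inflammatory markers at weeks 0, 4, 8 and 12, with PGIC from week 4.

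**The concern.** Stopping a drug and stopping observation are separate decisions, and the protocol merges them. For a woman removed part-way, the rescaled AUC lets her pain before removal stand for the whole 8 weeks. Section 8.3 does not say whether the target is pain while in the study or pain over all 8 weeks. The planned summary suits the first. The second cannot be produced, because no analysis recovers diaries that were never requested. Her remaining questionnaires go the same way.

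With 12 per arm and no replacement, each woman is 1/12, or 8.3%, of her arm. Section 8.2 says the results will inform the size of later work, so a distorted arm summary could carry forward. No confirmatory conclusion depends on it.

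**Working it through.** **The plan's own figures.** 12 per arm × 3 arms = 36, as in section 8.2 (1:1:1 allocation from 7.2.3). Screening at 50% failure: 36 / (1 − 0.5) = 72, against roughly 70 in section 8.1. Both reproduce, and the fix changes neither.

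**What is lost, and when.** The treatment period is 8 × 7 = 56 diary days. After baseline, LFTs and the C-SSRS are first done at week 4 (sections 7.2 and 7.2.4), so a removal they trigger normally falls at or after Visit 3.
- Diary days by Visit 3: 28/56 = 50.0%. With the ±3-day window: 25/56 = 44.6% to 31/56 = 55.4%.
- The Visit 3 questionnaires are completed "on-site prior to being discharged from the visit", so they are normally kept. The week-8 set is lost, which is 1 of 2 on-treatment assessments.
- Both on-treatment sets are lost only if removal comes before week 4, through a symptomatic event between visits. The patient education part of 7.2.3 gives that route.
- Removal after week 8 leaves the AUC complete and loses only week 12, when nobody is on study drug.

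**Gap between the two summaries.** The documents give no removal rate, timing or VAS values, so k, w and d are assumptions. With k women of 12 removed at week w, and later pain differing by d VAS points:

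shift in arm mean = (k/12) × ((8 − w)/8) × d; multiply by 7 for AUC per week.

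| k | w | d | VAS | AUC per week |
|---|---|---|---|---|
| 1 | 4 | 1 | (1/12)(4/8)(1) = 0.042 | 0.29 |
| 1 | 4 | 2 | (1/12)(4/8)(2) = 0.083 | 0.58 |
| 1 | 6 | 1 to 2 | 0.021 to 0.042 | 0.15 to 0.29 |
| 1 | 2 | 1 to 2 | 0.063 to 0.125 | 0.44 to 0.88 |

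The week-2 row needs a symptomatic event between visits.

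**Direction.** Two assumed courses for a woman removed on day 28:
- Pain would have fallen linearly from 6 (day 1) to 4 (day 56). Day-28 VAS = 6 − 2 × 27/55 = 5.018. Truncated weekly AUC = 7 × (6 + 5.018)/2 = 38.56. Full-period value = 7 × 5 = 35.0. The truncated value is higher by 3.56, or 3.56/12 = 0.30 on the arm mean.
- Pain is 4 on drug and returns to 6 afterwards. Truncated = 7 × 4 = 28.0. Full period = 7 × (4 × 28 + 6 × 28)/56 = 35.0. The truncated value is lower by 7.0, or 7.0/12 = 0.58 on the arm mean.

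The sign therefore depends on what happens to pain after removal, which the plan does not observe.

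**Precision of a week-8 secondary endpoint.** The 95% CI half-width for a two-arm difference is t(0.975, n1 + n2 − 2) × √(1/n1 + 1/n2), in SD units. It is 0.847 for 12 v 12, then 0.868, 0.893 and 0.923 if one arm loses 1, 2 or 3 women (assumed counts).

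**The case against.** **The plan already has an answer to early withdrawal.** Section 8.3 chose the weekly normalisation for this purpose, and pain while in the study is a defensible target for a pilot. Later diaries may reflect pain off study drug, off NETA or on other treatment. This stands: the normalised AUC is not wrong in itself, and the shifts above are gaps between two possible summaries, not errors in the planned one.

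**Removals may be few.** Section 3.2 excludes women with prior thromboembolic or arterial events, known liver disease, or recent suicidal ideation, who are risk groups for most of the listed events. Section 10.0 notes that the doses behind its transaminase rates were far above those planned. Women with the gravest events are also least able to keep a diary. This stands too, although migraine and Grade 3 events remain possible.

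**Cyclicity carries limited weight.** Women are to have been on NETA for 30 days before enrolment, with the dose adjustable to achieve amenorrhea. Removal at Visit 3 leaves about 28 diary days, roughly one cycle if a monthly cycle is assumed.

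**Stronger readings that the documents do not support.** A reader might infer that the mandatory removals in 3.3.1 are contradicted by section 9.3 ("potentially removed from the study if deemed medically necessary") and section 18.7 (the team will "determine whether the participant will need to be removed from the study or whether the study should be paused until further investigation"). Section 3.3.1 has its own discretionary tier for other adverse events, and both passages mostly fit it. A reader might also infer that 3.3.2 cancels the safety follow-up in 7.2.6 and 18.2. Read in order, its last sentence means nothing beyond the follow-up just listed. It could even be read as covering pregnancies only, but then no section provides for outcome collection after the other removals, and the gap is the same.

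**Conclusion.** The point holds as a design improvement. Safety removal ends outcome collection, so a removed woman's primary endpoint uses pre-removal days only, and full-period pain and later questionnaires are irrecoverable. The assumed one-woman illustrations give a shift of 0.02 to 0.13 VAS in an arm mean, or 0.04 to 0.08 (0.29 to 0.58 AUC per week) for removal at week 4. These rest on 12 women per arm and on assumed number, timing and pain change. The true frequency and direction are unknown.

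It would be going too far to say that the primary comparison is biased. Nothing in the documents shows how often removal will happen or that it will differ by arm: NETA is given in every arm, and unclear causality goes to study drug by convention. The distortion is possible and probably small. The case for acting is that the missing data cannot be rebuilt later, while collecting them leaves the planned summary available.

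**What to change.** In section 3.3.2, limit the closing sentence to women who withdraw consent, and state that safety follow-up continues. For women who stop study drug for safety and are able and willing:
- continue the automated daily diary to week 8 and the scheduled questionnaires, remotely if needed (sections 7.1 and 7.2 already provide emailed diary links and remote visits);
- take cytokine samples only if she attends a scheduled visit anyway;
- record the date study drug stopped, whether NETA stopped, and any new pain treatment.

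In section 8.3, report by randomised arm both the normalised AUC up to drug stop and the AUC using all collected diary days, and name the primary one in advance. The wording that links drug stopping to removal in 3.3.1 and 7.2.4 should be aligned with this continued collection. The criteria for stopping study drug are unchanged.

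The cost is protocol and consent wording plus modest follow-up effort, with the sample size still 36. The downside is noise in the all-days summary from pain off study drug, off NETA or on other treatment, and some women will be unable to continue.

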7.2.6 Study Visit 5 – 12 week (4 weeks post treatment)

The subject will return in 4 week. The study visit will be 3 days before or 3 days after this time to account for weekends. At this final study visit, we will collect final routine bloodwork (1) LFTs (2) inflammatory markers in addition to another urine toxicology and urine pregnancy test. This is be approximately 5-10cc of blood or 1-2 teaspoons. We will complete final surveys 1) EHP-30 (2) PGA (3) PGIC (4) C-SSRS (5) FSFI (if partnered and sexually active). Physical assessment will be performed as outlined in 7.2.3.

If the subject has any abnormal test results or adverse events, these will be followed until their resolution at time intervals deemed appropriate by the clinical team. If there is an unforeseen pregnancy, the pregnancy will be followed throughout for adverse maternal, fetal and neonatal outcomes.

7.2.7 (Optional) Study Visit 6 (Eligibility window: 12-24 weeks post-enrollment)

At the initial enrollment visit, all subjects will be offered participation in the optional pharmacokinetic testing. If interested, they will complete consent during the main consent process and we will recruit until we have enrolled four participants and they have completed this Visit. As we are recruiting from the study participants, who will have already undergone rigorous screening throughout the initial study, we will not be repeating any additional testing on these patient. During this part of the study, they will also only be receiving a one-time dose of CBD. They will remain eligible to participate in this study for up to 3 months from the date of their last visit.

After completion of the initial study, the participants will undergo a 4 week washout period of the study drug, which will correspond with Visit 5 (4 week post-treatment visit).

At this time, screening measures have been set forth by the institution to test for SARS-CoV2 (the virus that causes COVID-19) if a study participant is planning to stay overnight at the Clinical Research Center.

The subjects will be screened via telephone prior to testing.

- If negative, they will proceed to testing.
- If positive, they can be rescreened in 1 or more weeks. If negative, they can proceed to testing. This can continue until the participant is no longer eligible for this portion of the study.

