18.2 Recording of Adverse Events

All adverse events (serious or non-serious) and abnormal test findings observed or reported to study team believed to be associated with the study drug(s) or device(s) will be followed until the event (or its sequelae) or the abnormal test finding resolves or stabilizes at a level acceptable to the investigator.

An abnormal test finding will be classified as an adverse event if one or more of the following criteria are met:

- The test finding is accompanied by clinical symptoms
- The test finding necessitates additional diagnostic evaluation(s) or medical/surgical intervention; including significant additional concomitant drug treatment or other therapy
 NOTE: Simply repeating a test finding, in the absence of any of the other listed criteria, does not constitute an adverse event.

- The test finding leads to a change in study drug dosing or discontinuation of subject participation in the clinical research study
- The test finding is considered an adverse event by the investigator.

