18.3 Causality and Severity Assessments

The investigator will promptly review documented adverse events and abnormal test findings to determine 1) if the abnormal test finding should be classified as an adverse event; 2) if there is a reasonable possibility that the adverse event was caused by the study drug(s) or device(s); and 3) if the adverse event meets the criteria for a serious adverse event.

If the investigator's final determination of causality is "unknown and of questionable relationship to the study drug(s) or device(s)", the adverse event will be classified as associated with the use of the study drug(s) or device(s) for reporting purposes. If the investigator's final determination of causality is "unknown but not related to the study drug(s) or device(s)", this determination and the rationale for the determination will be documented in the respective subject's case history.

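### Section 3.3.2 ends data collection on removed women, while section 18.2 follows drug-associated adverse events to resolution, so how such an event ended could go unrecorded

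*Combined protocol and SAP*

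**What the plan says.** Section 3.3.1 lists the reasons for removing a woman from the study. They include known severe events of norethindrone acetate (NETA), such as stroke and deep vein thrombosis. They also include suicidal ideation and liver dysfunction, under the words "Serious adverse events associated with CBD include", and Grade 3 events attributed to study drug. For the last group it adds: "If causality cannot be determined, it will be attributed to the study drug".

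Section 3.3.2 says what happens next. Elevated liver tests are followed until they resolve, and pregnancies are followed for maternal, fetal and neonatal outcomes. For removal on any other 3.3.1 ground, "she will receive the appropriate treatment and follow up based on the decision of her providing physician team". The section ends: "No further data will be collected on these patients and the subject will not be replaced".

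Section 18.2 covers all adverse events and abnormal findings, serious or not, that are thought to be associated with study drug. It says they "will be followed until the event (or its sequelae) or the abnormal test finding resolves or stabilizes" at a level the investigator accepts. It does not exempt women who have been removed.

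**The concern.** Many of the women removed for safety under 3.3.1 are women whose events fall under 18.2, because the event was attributed to study drug. One section says to stop collecting data on them and the other says to keep following the event. The protocol does not say which governs.

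What is at stake is the end of the safety record, not its start. Under 9.3 the event is entered in REDCap, and under 3.3.1 the drug is stopped and the woman leaves the study. Whether the event then resolved, persisted or left sequelae, and when, depends on which section the coordinator reads. Section 2.2 states that there are no preliminary data on CBD for endometriosis pain and that the results may inform larger trials. How drug-attributed events ended is part of what those trials would want to know.

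**Working it through.** The plan gives no figure on this point, so the check compares the rules for each type of removal.

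| Reason for removal | Section 3.3.2 | Section 18.2 | Conflict? |
|---|---|---|---|
| Elevated liver tests | Followed until resolution | Followed if drug-associated | No, unless the closing sentence is read literally |
| Pregnancy | Followed for outcomes | Not the governing rule | No, with the same caveat |
| Suicidal ideation, listed in 3.3.1 as associated with CBD | Own physicians; no further data | Followed until resolved or stable | Yes |
| Grade 3 event attributed to study drug, including by default | Own physicians; no further data | Followed until resolved or stable | Yes |
| Listed NETA event, e.g. thromboembolism | Own physicians; no further data | Followed only if judged drug-associated | Only if so judged |
| Removal at the investigator's discretion | No study follow-up stated; no further data | Followed only if judged drug-associated | Only if so judged |
| Withdrawal of consent | No further data | Follow-up needs consent | No; stopping is appropriate |

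Two points limit the overlap. Under 18.3 the investigator judges causality case by case, so being listed in 3.3.1 does not by itself bring a NETA event under 18.2. The status of NETA is also unclear: 3.3.1 places it among the study drugs, while 7.2.1 and 7.4.5 treat it as standard of care. In the other direction, 18.3 classes events of unknown and questionable relationship as drug-associated for reporting.

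Next, does any other text settle the matter?

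- **7.2.6** says: "If the subject has any abnormal test results or adverse events, these will be followed until their resolution". This is stated for Visit 5, the final visit at week 12, and the section does not mention removed women.
- **18.4.1** requires follow-up safety reports, but only for suspected reactions that are both serious and unexpected. Under 18.1 an event already listed in the protocol, such as suicidal ideation, is not unexpected unless it differs in specificity or severity.
- **9.3** provides for recording adverse events and for forms that collect information over time. It does not override 3.3.2 for a removed woman.

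None of these resolves the conflict.

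An example shows the possible gap. Take a woman removed at Visit 3 (week 4) with a drug-associated event still ongoing. The last planned visit, Visit 5, is at week 12.

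- Time left to the last planned visit: 12 − 4 = 8 weeks.
- Section 7.2.3 plans adverse-event assessments at Visits 2 to 5, so those remaining are Visits 4 and 5 (weeks 8 and 12), which is 2.

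Under a literal 3.3.2, none of that period yields a study record of how the event ended. No rate or count of affected women is computed, because the plan gives no removal rate for its 36 randomized women.

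**The case against.** The strongest reply is that the literal reading defeats itself. The closing sentence of 3.3.2 would cancel the liver-test and pregnancy follow-up promised just above it, so it must mean something narrower, most naturally the diaries, surveys and cytokine samples. If liver-test follow-up survives the sentence, so can 18.2, which is the specific rule on adverse events. Section 18.2 also anticipates removal: it counts a test finding as an adverse event when that finding ends a woman's participation. Sections 9.2, 9.5, 18.7 and 19.1.2 add safeguards: detailed event descriptions, immediate notice of serious events to the principal investigator, a team meeting after major serious events, and a check that events are correctly entered. The physician-team sentence can be read as assigning clinical care only. Finally, 18.2 speaks of following events and does not name outcome or end date, and the REDCap forms are not in the documents.

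Much of this stands. The narrower meaning is probably the intended one, and staff may well keep following a serious event. The 8 weeks and 2 assessments show what could be missed and do not measure lost information, since an event might end within days.

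It does not remove the point. The sentence does not state its narrower meaning. Even if it did, 3.3.2 would still contrast liver tests, which the study follows, with every other ground for removal, which goes to the woman's own physicians with no route back to the study record. The safeguards do not address what is recorded after removal.

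**Conclusion.** The concern holds as a minor inconsistency. Followed as written, 3.3.2 would leave the study without the outcome and end date of a drug-associated event that caused removal. Followed as written, 18.2 would have the event pursued to its end. The conflict is confined to drug-associated events other than liver-test elevation in women who have not withdrawn consent.

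The number of such women is unknown and may be zero. No efficacy result or sample-size figure is affected, and the woman's treatment does not depend on it. The conclusion rests on site staff possibly taking 3.3.2 literally. If they all read it as covering scheduled data only and apply 18.2, nothing is lost.

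**What to change.** In 3.3.2, limit the closing sentence to efficacy, survey and other scheduled study data. Then add one sentence: adverse events thought to be associated with study drug and ongoing at removal, including those attributed by default under 3.3.1, are followed under 18.2 and their outcome and end date recorded, unless the woman withdraws consent. Keep the liver-test and pregnancy provisions as they are.

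The cost is that wording and a few extra contacts with removed women. No new procedure is needed, because 18.2 already commits the site to this follow-up.
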